6.3.2. Safety

The SCCS design inherently controls for fixed individual-level confounders. With comparison periods before and after the risk period, the design also controls for time-varying covariates such as age and seasonality.

7. STUDY POPULATION

7.1. Demographics

Table 2 shows the characteristics of individuals with RA and IBD by RZV vaccination status as of 1/1/2020, thus is not indicative of the entire study population. Most of the individuals with RA who were unvaccinated were 50 years or older (80.3%), female (80.7%), and Hispanic or White (78.5%), while most individuals with RA who were vaccinated were 50 years or older (98.8%), female (80.7%), and White or Hispanic (74.5%). In those with IBD for both the vaccinated and unvaccinated, approximately half of the group was female and half male, while over 50% were White in both groups. Due to the expanded indication in July 2021 and new recommendations in October 2021 for RZV vaccination in those ≥ 18 years of age who are or will be at increased risk of HZ due to immunodeficiency or immunosuppression caused by known disease or therapy, the number of vaccinated individuals 18-49 years of age is expected to increase after 2021.

Table 2 Demographic characteristics of RZV unvaccinated and vaccinated individuals with RA and IBD at KPSC as of 1/1/2020

	Rheumatoid arthritis				Inflammatory bowel disease ¹			
	Unvaccinated ²		Vaccinated ³		Unvaccinated ²		Vaccinated ³	
	N	Percent	N	Percent	N	Percent	N	Percent
Age at index date (years)								
18-49	2831	19.7	15	1.2	3923	44.4	30	3.9
50-69	6758	47.0	611	49.6	3166	35.9	401	52.5
≥ 70	4797	33.3	607	49.2	1742	19.7	333	43.6
Sex								
Female	11616	80.7	995	80.7	4475	50.7	412	53.9
Male	2770	19.3	238	19.3	4356	49.3	352	46.1
Race/ethnicity								
Asian	1104	7.7	182	14.8	555	6.3	58	7.6
Black	1570	10.9	107	8.7	840	9.5	38	5.0
Hispanic	6265	43.6	340	27.6	2167	24.5	97	12.7
Multiple/Other/ Unknown	432	3.0	26	2.1	351	4.0	12	1.6
White	5015	34.9	578	46.9	4918	55.7	559	73.2
Charlson comorbidity index⁴								
0	0	0.0	0	0.0	4157	47.1	199	26.1
1-2	8645	60.1	649	52.6	3175	36.0	331	43.3
3-4	3645	25.3	361	29.3	999	11.3	165	21.6
5 or higher	2096	14.6	223	18.1	500	5.7	69	9.0
Total	14386	100	1233	100	8831	100	764	100

CD = Crohn's disease; IBD = inflammatory bowel disease; KPSC = Kaiser Permanente Southern California; N = number; RA = Rheumatoid arthritis; RZV = Recombinant Zoster Vaccine; UC = ulcerative colitis

¹IBD includes UC and CD.

²Index date was 1/1/2020. Individuals had ≥ 1 year of KPSC membership prior to index date, had ≥ 2 diagnoses of the autoimmune condition in the year prior to index date, and never received RZV prior to 2020.

³Index date was date of the first RZV dose from 4/2018-12/2019. Individuals had ≥ 1 year of KPSC membership prior to index date and had ≥ 2 diagnoses of the autoimmune condition in the year prior to index date.

⁴Charlson comorbidity index is based on data in the 1 year prior to index date. It includes connective tissue disease-rheumatic disease, and all RA patients had 2 or more rheumatic disease codes in the 1 year prior to index date.

As of January 1, 2018, KPSC membership consisted of 1,495,838 KPSC members aged 50 years and older, 899,592 members aged 60 years and older, and more than 130,000 members aged 80 years and older (Table 3). Approximately 53% of KPSC members were female, and the racial/ethnic composition included White (43%), Hispanic (30%), Asian/Pacific Islander (11%), and African American (9%). Geographically, KPSC covers the entire Southern California region from Bakersfield to San Diego.

Table 3 Demographic distribution of KPSC members 50 years and older on January 1, 2018

Age on January 1, 2018 (years)	Frequency	Percent
50-59	596,246	39.86
60-69	493,190	32.97
70-79	275,722	18.43
80+	130,680	8.74
Sex		
Female	793,381	53.04
Male	702,457	46.96
Race/Ethnicity¹		
White	636,438	42.55
Hispanic	452,243	30.23
Asian and Pacific Islander	167,298	11.18
African American	138,879	9.28
Multiple/other/unknown	100,980	6.75
Total	1,495,838	100

¹All categories other than Hispanic are non-Hispanic ethnicity.

Table 4 shows the length of retention of KPSC membership by age group beginning January 1, 2008. Approximately 52% of members aged 50-59, 61% of members aged 60-69 years, and 57% of members aged 70-79 years had completed 10 years of membership at KPSC. For members aged 80 years and older, the percentage of members who completed 10 years of membership at KPSC decreased to 24%. The stability of KPSC membership allows the unique opportunity to follow patients over time and conduct long-term effectiveness studies.

Table 4 Prospective length of KPSC membership among individuals aged ≥50 years on January 1, 2008

		Membership length (years)			Total
		0-5	>5-10	>10	
Age on January 1, 2008 (years)					
50-59	N	145,613	77,164	239,563	462,340
	Row %	31.49	16.69	51.82	
60-69	N	76,378	37,055	176,036	289,469
	Row %	26.39	12.8	60.81	
70-79	N	33,640	34,072	88,441	156,153
	Row %	21.54	21.82	56.64	
80+	N	34,335	23,808	18,309	76,452
	Row %	44.91	31.14	23.95	
Total	Frequency	289,966	172,099	522,349	984,414

7.2. Inclusion and exclusion criteria (Eligibility criteria)

7.2.1. Inclusion criteria

Individuals with at least 2 health care encounters with assigned ICD-10 codes for RA or IBD (UC or CD) in the year prior to and including the index date will be identified from the EHR, as specified below. This algorithm was selected based on the literature [MacLean, 2000; Weng, 2007] and KPSC chart review indicated a high positive predictive value of this approach.

Rheumatoid arthritis ICD-10 Codes

- M05.* - Rheumatoid arthritis with rheumatoid factor
- M06.* - Other rheumatoid arthritis

Crohn's disease ICD-10 Codes

- K50.* - Crohn's disease

Ulcerative colitis ICD-10 Codes

- K51.* - Ulcerative colitis

The population for primary VE objective 1, secondary VE objectives 2 and 4-6, and exploratory VE objectives 1 and 3 will be drawn from individuals with RA, and the population for primary VE objective 2, secondary VE objectives 1, 3-5, and 7, and exploratory VE objectives 2 and 4 will be drawn from individuals with IBD (UC or CD).

Similarly, the population for primary safety objective 1 and exploratory safety objective 1 will be drawn from individuals with RA, and the population for primary safety objective 2, secondary safety objective 1, and exploratory safety objective 2 will be drawn from individuals with IBD (UC or CD).

While co-occurrence of both conditions in the same individual is expected to be rare, individuals with both RA and IBD will be included in analyses for both conditions.

Individuals will be included in the study if they meet the following criteria:

VE

- Aged ≥ 18 years at index date
- At least 1-year of continuous KPSC membership prior to the index date and until 31 days after index date (allowing for a 31-day gap in membership)

Safety

- Received ≥ 1 dose of RZV
- Aged ≥ 18 years at date of first RZV dose
- At least 1-year continuous KPSC membership prior to date of first RZV dose (allowing for a 31-day gap in membership)

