6.1.2. Safety

An SCCS design (Figure 1) will be used. For patients receiving only 1 dose of RZV, the date of vaccination with the first dose of RZV will be defined as Day 0, the risk period will be defined as +1 to +30 days, and comparison periods will be defined as -90 to -61 days and +31 to +60 days (Figure 1, Individuals received only one dose). The washout period will be defined as -60 to -1 days. The 30-day risk period was determined based on prior literature, vaccine mode of action, and consultation with external physician experts (rheumatologists and gastroenterologists) [Basra, 2012; Didierlaurent, 2017].

For individuals who receive a second dose of RZV within 300 days of the first RZV dose, there are several scenarios for additional risk and comparison periods. If the second dose is received between +28 to +90 days after the first dose, the risk period after the first dose will be immediately followed by a washout period up to receipt of the second dose (Figure 1, Scenario 1). If the second dose is received between +91 to +150 days after the first dose, the risk and comparison periods following the first dose will be followed by a 60-day washout period immediately before the receipt of the second dose (Figure 1, Scenario 2). If the second dose is received between +151 days to +300 days after the first dose (expected to be less common), there will be a comparison period -90 to -61 days prior to the second dose and a washout period -60 to -1 days prior to the second dose (Figure 1, Scenario 3). In Scenario 1, the risk window after the first dose could be between 28 and 30 days and the subsequent washout window could be between 0 and 60 days. In Scenario 2, the comparison window between 2 doses could be between 1 and 60 days. The maximum follow-up period will be 360 days after the first dose. Scenarios 2-4 in Figure 1 represent the maximum time period between the first and second dose

Figure 1 SCCS Design Overview for Safety Analysis

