13.1.2. Glossary of terms

Day 0	For safety objectives, the date of vaccination with the first dose of RZV
Flare	Clinically relevant new-onset flare or new-onset disease worsening of RA or IBD (UC or CD) (Appendix 2)
HZ	Herpes zoster (shingles), an often painful vesicular rash caused by reactivation of VZV persisting latently in dorsal root ganglia
Index date	For 2-dose RZV VE objectives, the index date is the date of receipt of the second dose of RZV for vaccinated individuals and their unvaccinated matches. For 1-dose RZV VE objectives, the index date is the date of receipt of the first dose of RZV for vaccinated individuals and their unvaccinated matches.
PHN	Neuropathic pain that arises from sensory (dorsal root or trigeminal ganglion cells). HZ-related pain persisting ≥ 3 months after HZ diagnosis.
RZV	A 2-dose subunit zoster vaccine containing recombinant glycoprotein E in combination with a novel adjuvant

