13.2. Appendix 2: Definition of clinically relevant flare

Definition of “clinically relevant” flare

For this study, flare is defined as clinically relevant new-onset flare or new-onset disease worsening of RA (primary safety objective 1, exploratory safety objective 1) or IBD (UC or CD) (primary safety objective 2, secondary safety objective 1, exploratory safety objective 2). This definition was selected in consultation with rheumatologist and gastroenterologist experts, recognizing that new-onset disease worsening can be difficult to differentiate from flare. Trained research associates and RA or IBD specialists will review all potential flare events, according to the following case definition:

1. Contact with health care provider via documented phone call, email, telehealth visit, or in-person office, Emergency Department, or inpatient visit, AND
2. New or worsening signs and/or symptoms suggestive of a flare (at least one of the signs or symptoms below):
 - a. RA – joint swelling, joint pain/tenderness, joint stiffness.
 - b. IBD – abdominal pain/tenderness, diarrhea (increased stool frequency and/or soft or liquid stool), urgency, rectal bleeding, blood in stool, nausea/vomiting, unintentional weight loss.
 - c. Provider mention of flare, worsening of disease, recurrence, or relapse

AND

1. Change in medication for flare*:

Proposed medication regimen change/escalation algorithm for flare

- a. Intra-articular corticosteroid joint(s) injection (for RA), or
- b. Initiation of systemic corticosteroid (e.g., prednisone), or
- c. Increase in dose of baseline systemic corticosteroid (e.g., prednisone 5 mg daily to prednisone 40 mg daily with taper), or
- d. Switch in methotrexate (MTX) from oral route to subcutaneous (for RA), or
- e. Increase in dose and/or frequency of administration of any medication in current baseline regimen, or
- f. Addition of another medication to current medication regimen (e.g., MTX to current regimen of hydroxychloroquine [(Plaquenil)], biologic to current regimen of MTX), or
- g. Switch of a current medication to another medication, in the same or different category (e.g., MTX + tumor necrosis factor [TNF]-alpha inhibitor to MTX + tofacitinib; MTX + TNF-alpha inhibitor to MTX + a different TNF-alpha inhibitor)

*Exclude medication changes for any reasons other than for flare, such as acute kidney injury or other adverse effects from prior medication.

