Chart review will be performed among individuals eligible for the safety analysis. Trained research associates will review medical records from health care encounters during risk windows, comparison windows, and the 30 days after a risk or comparison window (while masked to the precise window) for evidence of flare. They will identify new or worsening signs and/or symptoms suggestive of a flare and capture the date of onset of new or worsening signs and/or symptoms. They will determine whether a change in medication was made for flare by a provider. Cases with unclear sign and/or symptoms, date of onset, or change in medication for flare will be reviewed by an RA or IBD specialist.

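### The safety eligibility lookback includes the pre-dose comparison window but not the risk window, so a pre-dose flare can make a patient eligible; taken alone, this lowers the flare RR by an amount the protocol does not determine

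*Protocol*

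**What the plan says.** Section 7.2.1 sets one disease rule for the VE and safety populations: at least two "health care encounters with assigned ICD-10 codes for RA or IBD (UC or CD) in the year prior to and including the index date". It applies the rule to safety by stating that "the population for primary safety objective 1 and exploratory safety objective 1 will be drawn from individuals with RA", with a parallel statement for IBD.

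The safety anchor has to be inferred. The glossary (13.1.2) defines the index date only for the VE objectives. For safety it defines Day 0: "For safety objectives, the date of vaccination with the first dose of RZV". The age and membership criteria for safety in 7.2.1 also run from the first dose, and Table 2 indexed vaccinated patients at the first dose under the same two-diagnosis rule. Section 11.2.4 uses the term index date for the exploratory safety objectives without defining it.

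For one-dose patients, section 6.1.2 sets the risk period at +1 to +30 days and says "comparison periods will be defined as -90 to -61 days and +31 to +60 days". It adds: "The washout period will be defined as -60 to -1 days".

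The first element of the flare definition in Appendix 2 is "Contact with health care provider via documented phone call, email, telehealth visit, or in-person office, Emergency Department, or inpatient visit". The same appendix says "Chart review will be performed among individuals eligible for the safety analysis". The ENCePP checklist (13.5.8, item 10.8) records that no sensitivity analyses are planned.

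**The concern.** SCCS conditioning removes differences between patients that are fixed over time. It does not remove selection that depends on when the event happened, and that is the kind of selection at issue here.

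Consider a patient with one other coded visit in the year. With a flare on Days -90 to -61 that is seen and coded, the patient reaches two codes and enters. With the same flare on Days +1 to +30, the patient has one code at Day 0 and never enters. Only eligible patients have their charts reviewed, so those left out are not recovered later.

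No diagnosis before Day -90 is required. A patient first presenting and first treated with systemic corticosteroid on Days -90 to -61 could therefore also be counted as a comparison-window flare. How often that would happen is not known.

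The effect is extra events in one comparison window and none in the risk window. For a safety question, an RR pulled downward could hide a real increase in flares.

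**Working it through.** **1. Which windows the lookback covers.** Take the first dose as Day 0.

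| Window (one-dose patient) | Days | Inside the qualifying year? |
|---|---|---|
| Comparison, pre-dose | -90 to -61 | Yes |
| Washout | -60 to -1 | Yes, but flares with onset here are not counted |
| Risk | +1 to +30 | No |
| Comparison, post-dose | +31 to +60 | No |

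Appendix 2 reviews encounters up to 30 days after each window. For the pre-dose window that ends at Day -31, still inside the lookback. The washout therefore does not stop codes from a pre-dose flare counting toward eligibility. A flare is dated by symptom onset, so the encounters for a risk-window flare fall after Day 0.

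**2. The plan's own figures (section 11.1.2).** The signed root likelihood ratio formula with k = 2, r = 1/(1+k) = 1/3 and RR = ρ is:

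- A = 2[(ρr/(ρr+1−r))·ln ρ − ln(ρr+1−r)]
- B = ((ln ρ)²/A)·ρr(1−r)/(ρr+1−r)²
- n = (1.960 + 0.842·√B)²/A

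At ρ = 1.5, A = 0.0392, B = 1.026 and n = 201.6, against 87 + 115 = 202 in Table 7. For RR 1.2, 2 and 3 the totals are 1029.2, 67.0 and 26.3, against 1029, 68 and 26. Expected comparison flares also reproduce: 3071 × 0.025 × 2 = 153.6 (stated 154) for RA and 2308 × 0.03 × 2 = 138.5 (stated 138) for IBD. All of these assume the same baseline flare rate in both comparison windows.

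**3. Effect on the RR.** Let S = P(eligible | flare in -90 to -61) / P(eligible | no flare there), and let λ be the flare rate per 30 days. Among included one-dose patients the pre-dose window has rate Sλ, the post-dose window λ and the risk window RR·λ. The comparison average is λ(1+S)/2, so

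observed RR = true RR × 2/(1+S).

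**4. Size of S (assumption).** The protocol gives no distribution of coded encounters. For illustration, let coded encounters apart from the flare be N ~ Poisson(m) per year. If the flare adds one code, S = P(N≥1)/P(N≥2). If it adds two, S = 1/P(N≥2).

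| m | P(N≥1) | P(N≥2) | S (1 code; 2 codes) | True RR 1 becomes | True RR 1.5 becomes |
|---|---|---|---|---|---|
| 2 | 0.865 | 0.594 | 1.46; 1.68 | 0.81; 0.75 | 1.22; 1.12 |
| 3 | 0.950 | 0.801 | 1.19; 1.25 | 0.91; 0.89 | 1.37; 1.33 |
| 4 | 0.982 | 0.908 | 1.08; 1.10 | 0.96; 0.95 | 1.44; 1.43 |
| 6 | 0.998 | 0.983 | 1.02; 1.02 | 0.99; 0.99 | 1.49; 1.49 |

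**5. Effect on power at true RR 1.5.** This uses the same formula and the protocol's inputs (RA 3071 at 2.5%; IBD 2308 at 3%).

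| S | RA | IBD |
|---|---|---|
| 1.00 | 0.90 | 0.87 |
| 1.05 | 0.86 | 0.83 |
| 1.10 | 0.82 | 0.78 |
| 1.25 | 0.66 | 0.61 |

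Using only the post-dose comparison window (k = 1) removes this mechanism, with power of about 0.80 (RA) and 0.75 (IBD).

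**6. What a lookback ending at Day -91 would lose.** Days -365 to -91 are 275 of the 366 days, so the mean becomes 0.751m. The proportion lost is 1 − P(N'≥2)/P(N≥2), with N' ~ Poisson(0.751m).

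| m | Patients lost | Comparison flares left: RA | IBD |
|---|---|---|---|
| 2 | 25% | about 115 | about 103 |
| 3 | 18% | about 126 | about 114 |
| 4 | 12% | about 136 | about 122 |
| 6 | 4% | about 147 | about 132 |

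Section 11.1.2 requires 115 for RR 1.5.

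**The case against.** The strongest objection concerns size. The large distortions need m = 2, where 41% of patients (1 − 0.594) would fail the two-code rule without the flare. At m = 4 to 6 the null RR is 0.95 to 0.99, small beside a design target of 1.5. Three features of the model could also overstate the effect. If patients who flare are seen more often than average, most qualify anyway. A phone call or email satisfies the flare definition but may carry no ICD-10 code. Two-dose patients whose second dose falls at +91 to +300 days (Scenarios 2 and 3 in section 6.1.2) gain comparison time between doses, which dilutes the affected window; Scenario 1 gives no clear dilution. All of this stands as a limit on size. None of it removes the asymmetry.

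A second objection concerns direction. A reader might infer that the reported RR will be biased toward no harm. The protocol does not support that as a net statement. Patients who qualify through active disease just before Day 0 could flare again soon after it, which would raise the RR. So would vaccination deferred because of a flare, to the extent that the 60-day washout does not absorb it. Only the direction of this one mechanism is established.

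Third, the anchor is inferred. If the second dose were meant, a flare after the first dose could also qualify a patient and the argument would change. The first dose is much the better supported reading, but the text should say so.

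**Conclusion.** The point holds as a design weakness of unknown size. Read with the first dose as the safety index date, section 7.2.1 lets outcome events in one comparison window contribute to inclusion and gives risk-window events no such role. For both primary safety objectives this mechanism alone lowers the RR by the factor 2/(1+S) in one-dose patients, and generally by less where there is comparison time between doses. Under the assumed Poisson model the factor runs from 0.75 to 0.99. It matters if many patients are close to the two-code threshold and is negligible if most have several coded visits a year. The sponsor can measure this; the protocol does not report it.

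A reader might also infer that the primary eligibility rule must be replaced at once and at little cost. The figures do not support that: where the bias is large, the shorter lookback also loses the most patients, enough to take the IBD comparison flares below 115 at m = 2 and m = 3.

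**What to change.** - State in 7.2.1 and the glossary that the index date for the safety objectives is the first-dose date.
- Prespecify, for both primary safety objectives, an SCCS analysis restricted to patients with two coded encounters on Days -365 to -91, and report it beside the current-rule estimate. Amend checklist item 10.8 accordingly.
- As a further check, add an analysis using only post-dose comparison time.
- Report how many patients lose eligibility under the restricted rule. Make that rule primary if enough events remain, taking the protocol's own 115 comparison-window flares for RR 1.5 as the mark.
- Leave the VE rule unchanged.

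The cost is an added analysis on data already held. The existing one-year membership requirement covers the restricted lookback, and completed chart reviews remain usable. The restricted set loses low-utilising and newly diagnosed patients, about 4% to 25% under the assumed model. It also uses a shorter lookback than the one-year algorithm whose positive predictive value was checked by chart review, which is a reason to report both estimates.

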7.2.2. Exclusion criteria

For both VE and safety objectives, individuals who receive a second dose less than 4 weeks (i.e., 28 days) after the first dose will be excluded, since ACIP guidelines state that these individuals must repeat the second dose [Dooling, 2018].

For the VE objectives, individuals with an HZ diagnosis in the 6 months prior to the index date will be excluded to ensure that HZ diagnoses after the index date are new, rather than carried over from HZ episodes prior to the index date. Individuals with HZ occurring within 30 days after the index date for both vaccinated and unvaccinated groups will also be excluded since it is unclear if the HZ episode began before or after the index date and whether the length of time since vaccination (for RZV vaccinated individuals) is long enough to allow for sufficient development of immunity. Individuals with receipt of zoster vaccine within 30 days after index date will be excluded. Individuals with a death date within 30 days after index date will be excluded.

7.3. Number of participants

Detailed in Section 11.

7.4. Matching for VE analyses

For secondary VE objectives 1-3, secondary VE objective 5, and exploratory VE objectives 1-4, individuals meeting inclusion criteria who receive 2 doses of RZV at least 4 weeks apart through the end of the accrual period will be matched with unvaccinated individuals who have not received any doses of RZV as of the index date at a ratio of 1 to up to 3. For secondary VE objective 4, individuals meeting inclusion criteria who receive 2 doses of RZV >6 months apart through the end of the accrual period, and for primary VE objectives 1-2, individuals meeting inclusion criteria who receive 2 doses of RZV 4 weeks to 6 months apart, and their respective matched unvaccinated comparators will be included. No separate matching is needed.

Matching variables will comprise the following:

- Condition (RA, UC, CD)
- Age (by decade) at index date
- Sex
- Race/ethnicity, if sample size allows
- Medication category at index date (detailed in [Appendix 3](#)).

For secondary VE objectives 6-7, individuals who receive 1 dose of RZV but do not receive a second dose 4 weeks to 6 months after the first dose will be matched with unvaccinated individuals who have not received any doses of RZV as of the index date at a ratio of 1 to up to 3. The 1-dose person-time will be censored upon receipt of the second RZV dose received >6 months after the first dose. Matching variables will comprise condition (RA, UC, CD), age (by decade) at index date, sex, race/ethnicity (if sample size allows), and medication category at index date.

The 2-dose (4 weeks to 6 months) RZV cohort and 1-dose RZV cohort will be mutually exclusive. Unvaccinated individuals who are matched to RZV vaccinated individuals can contribute person-time to a vaccinated cohort if they receive RZV; their unvaccinated person-time is censored upon receipt of the first dose of RZV.

